10.2.2 Effectiveness Analysis

The primary analysis timepoint for effectiveness is 6 months post TIF procedure. Descriptive summaries as described in 10.2.1 General Methodology will be provided for the primary effectiveness endpoint of proportion of patients with normalized esophageal acid exposure, and secondary endpoints of proportion of patients free of “troublesome” symptoms and proportion of patients with a clinically significant reduction in PPI consumption from their pre-TIF screening consumption.

At each assessment time point, RDQ, atypical symptom RSI, Quality of Life questionnaires GSRS, HRQL will summarized as continuous measures. At 6 months, changes from baseline will be similarly summarized for each of these instruments. As defined in Section 8.1, portions of patients with clinically significant improvements will also be reported with 95% confidence intervals for GERD-HRQL, GERD-GSRS, RSI, and RDQ.

In addition, for the primary endpoint, proportion of patients with normalized esophageal acid exposure, 44% was observed in the EGS RESPECT study. Non-inferiority testing will be conducted for the same proportion observed in the HEURISTIC study vs. the RESPECT result. The hypotheses are as follows.

H_0 : HEURISTIC 6-month normalization rate $\leq 44\% - 20\% = 24\%$

H_A : HEURISTIC 6-month normalization rate $> 44\% - 20\% = 24\%$

The HEURISTIC normalization rate will be considered non-inferior to the 44% RESPECT rate if H_0 can be rejected at a 1-sided $p < 0.05$ level by exact binomial

probability calculation. To achieve this goal in 50 evaluable patients, the observed 6-month normalization rate in HEURISTIC must be 18/50 (36%) or higher.

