Study Hypotheses	
Primary Effectiveness hypothesis At 6-month follow-up, the proportion of TIF patients with normalized esophageal acid exposure will be statistically non-inferior to results from the EGS RESPECT study.
 
Secondary Effectiveness hypothesis 1 The proportion of TIF patients who are free of “troublesome” symptoms will be the same as or higher than the EGS RESPECT study.
 
Secondary Effectiveness hypothesis 2 At 6-month follow-up, $\geq 50\%$ of the TIF patients will have a clinically significant reduction in PPI consumption as compared with their pre-TIF consumption.
 
Primary Safety hypothesis 1 At 6-month follow-up, no increase in medically significant AE's as compared with the RESPECT study
 
Secondary Safety hypothesis 1 At 6-month follow-up, no new onset symptoms and side effects frequently associated with Nissen fundoplication procedures including dysphagia and gas bloat.

-------------------------	---

Table of Contents

Protocol Approval Page	2
Investigator's Signature Page	3
Table of Contents.....	8
1. Introduction and History of Prior Investigations.....	11
2. Device Description	13
3. Study Design Rationale	14
4. Study Objective	15
5. Study Hypotheses	15
5.1. Primary Efficacy Hypothesis 1.....	15
5.2. Secondary Efficacy Hypothesis 1	15
5.3. Secondary Efficacy Hypothesis 2.....	15
5.4. Primary Safety Hypothesis 1	15
5.5. Secondary Safety Hypotheses 1	16
6. Study Design	16
6.1. Study Population.....	16
6.2. Study Schematic Design.....	16
7. Study Population	18
7.1. Selection Criteria	18
7.2. Withdrawal	19
8. Study Methods and Techniques	19
8.1. Clinical Symptom Assessments.....	19
8.2. PPI Usage	19
8.3. Upper GI Endoscopy	20
8.4. BRAVO pH Studies.....	21
8.5. Esophageal Motility.....	21
9. Study Procedures	21
9.1. Determination of Patient Eligibility – Screening Process	23
Initial Screening -	23
Final Screening :-	23
9.2. Prior to the Study Procedure.....	23
9.3. During the Study Procedure	23
TIF Procedure (Treatment).....	24
9.4. Post-Procedure / Hospital Discharge	25
9.5. Follow-up.....	25
10. Statistical Considerations	26
10.1. Analysis Populations and Missing Data Handling	26
10.2. Statistical Analysis Plan	26
10.1. Sample Size and Power Estimation	27
11. Clinical Effectiveness Endpoints and Evaluation Criteria	27

11.1. Clinical effectiveness.....	27
12. Risks	28
13. Adverse Events.....	29
13.1. Causality and Seriousness Assessment.....	29
13.2. Reporting Serious Adverse Events	30

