Patients	2:1 ratio TIF/Placebo group (n=80) vs. Sham/PPI group (n=40)	2:1 ratio TIF group (n=28) vs. PPIs group (n=14)	1:1 ratio TIF group (n=22) vs. sham group (n=22)	274 patients treated with TIF procedure	1:1 ratio TIF group (n=250) vs. LNF group (n=250)
Duration(s)	6 months, 1 year w/ crossover (abstract)	6 months, 1 year w/ crossover, 3 years	6 months	6 months, 1 year, 2 years	Ongoing
Key Outcomes	
 ✓ Troublesome regurgitation was eliminated in 72% of TIF patients at > 1Y ✓ Median heartburn score decreased from 17 to 5 at 6 months and to 3, at > 1Y post-TIF ✓ Complete cessation of PPI therapy was achieved in 72% of TIF patients > 1Y 	
 ✓ All symptomatic outcome measures were stable between 1Y, 2Y and 3Y follow-up ✓ Esophagitis was healed in 86% of patients at 3Y follow-up ✓ 71% of patients completely off PPIs at 3Y follow-up ✓ Improvement in pH parameters remained stable at 3Y follow-up 	
 ✓ Average of 197 days “time in remission” post-TIF vs. 107 days post-sham ✓ Six months post-op 13/22 (59%) of TIF patients were in clinical remission with complete cessation of PPIs consumption. ✓ 69% of the TIF group normalized esophageal acid exposure vs. 20% of the sham group 	At 2Y follow-up: 
 ✓ 65% normalization in the Reflux Symptom Index score ✓ 74% normalization of Gastroesophageal Reflux Symptom Score ✓ A decrease from 91% to 29% in daily PPI use ✓ 75% of patients had esophagitis healed 	In enrollment

Table 2. Summary of Level I and II Clinical Studies (TIF 2.0)

2. Device Description

The EsophyX® Z device is a single use, hand-held flexible instrument that is introduced transorally with a flexible endoscope in the center of the device, so the entire procedure can be done safely under direct visualization. The device is designed so the physician can manipulate esophageal and gastric tissue, creating a partial fundoplication, secured by and deploy strong, H-shaped fasteners in order to reconfigure lower esophageal anatomy to prevent GERD.

3. Study Design Rationale

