In this context, an ideal study would consist of enrolling patients who suffered from persistent troublesome symptoms while on optimized dose of PPIs. The prospective study is open-label, non-randomized, and investigator initiated at multiple (3) sites (n=50). The primary endpoint is a clinically significant pH improvement, i.e. normalization, at the 6 month post-op mark. The proportion of patients with normalized esophageal acid exposure after 6 months will be compared to that of the previous EsophyX RESPECT trial to demonstrate equivalent (non-inferior) effectiveness. A sequence of follow-up visits will be required (2 week, 3 month, 6 month) to monitor symptom presence and PPI intake via Quality of Life surveys in addition to the primary endpoint. This follow-up and symptom monitoring will include evaluation of potentially new onset symptoms such as dysphagia and gas bloating commonly associated with the NF procedure.

4. Study Objective

Evaluation of the relative merits, safety and effectiveness of the EsophyX Z transoral device in performing an advanced TIF procedure preceded by laparoscopic Hiatal Hernia repair (hiatal hernias >2cm and \leq 4 cm) in PPI- prescribed patients with “troublesome symptoms” per the Montreal consensus definition.

5. Study Hypotheses

5.1. *Primary Efficacy Hypothesis 1*

At 6-month follow-up, the proportion of TIF patients with normalized esophageal acid exposure will be statistically non-inferior to results from the EGS RESPECT study.

5.2. *Secondary Efficacy Hypothesis 1*

The proportion of TIF2 patients who are free of “troublesome” symptoms will be the same as or higher than the results from the EGS RESPECT study.

5.3. *Secondary Efficacy Hypothesis 2*

At 6-month follow-up, \geq 50% of the TIF patients will have a clinically significant reduction in PPI consumption as compared with their pre-TIF consumption

5.4. *Primary Safety Hypothesis 1*

At 6-month follow-up, no increase in medically significant adverse events as compared with the RESPECT study

5.5. *Secondary Safety Hypotheses 1*

[figure not shown]
At 6-month follow-up, no new onset symptoms and side effects frequently associated with Nissen fundoplication procedures including dysphagia and gas bloat.

6. Study Design**6.1. *Study Population***

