10.2.3 Safety Analysis

Treatment emergent adverse events, i.e. adverse events occurring during or after the first protocol procedure (i.e. hiatal hernia reduction), will be summarized. The proportion of patients with medically significant adverse events will be compared to the same proportions observed in the RESPECT study.

In addition, the number and proportion of subjects reporting any given adverse event, including any clinically significant hiatal hernia repair complications and new onset symptoms (dysphagia, gas bloat) should they occur, will be tabulated. Separate tables will be constructed for (a) all reported treatment emergent adverse events, (b) protocol procedures (hiatal hernia reduction, TIF) related adverse events, and (c) serious adverse events.

10.1. *Sample Size and Power Estimation*

For the primary endpoint, proportion of patients with normalized esophageal acid exposure at 6 months post TIF procedure, 44% was observed in the EGS RESPECT study. It is assumed that the true underlying rate for HEURISTIC treatment would be the same, i.e. 44%. In order to reject an inferior normalization rate of 24% at a 1-sided $p < 0.05$ level, the observed 6-month normalization rate in HEURISTIC must be 18/50 (36%) or higher. With 50 evaluable subjects, the chance (power) for successfully reaching this goal is 0.90.

11. Clinical Effectiveness Endpoints and Evaluation Criteria

11.1. *Clinical effectiveness*

Primary effectiveness endpoint and evaluation criterion

The primary efficacy endpoint is normalization in esophageal acid exposure at 6 months post TIF procedure. Normalization in esophageal acid exposure is defined as $\leq 5.3\%$ of time with $\text{pH} < 4$ in a 48-hour monitoring period.

Secondary effectiveness measures and evaluation criteria

Secondary effectiveness measures include free of “troublesome” heartburn and/or regurgitation symptoms and a clinically significant reduction in PPI use.

Per Montreal Consensus definition, troublesome symptoms are mild to severe symptoms which occur a minimum of 2 days a week.

A clinically significant PPI consumption reduction is defined as from daily use to occasional use or none at all. Daily use is defined as a double dose, or full dose or half dose taken daily for more than 80 % of the total number of days during the proceeding follow-up period.

Table 5. Study Effectiveness Endpoints and Success Criteria

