Study Endpoints/Outcomes	Control	Pre-procedure Value	Post-procedure Value	Success Criteria
PRIMARY EFFECTIVENESS				
Normalized acid exposure	Self-Comparison	BRAVO Ph studies after off anti-secretory meds ≥ 7 days	BRAVO Ph studies at 6 months after off anti-secretory meds ≥ 7 days	Treatment success will be defined by a proportion of TIF patients with normalized acid exposure that is non-inferior to the RESPECT result as defined in 10.2.2.
SECONDARY EFFECTIVENESS				
GERD symptoms	Self-Comparison	Reflux Disease Questionnaire (RDQ) scores	Reflux Disease Questionnaire (RDQ) scores at and 6 months	Treatment success will be defined by a proportion of TIF patients free of troublesome symptoms at 6 months that is \geq the same proportion in RESPECT Trial (67%)
PPI usage	Self-Comparison	PPI usage (must be "daily")	PPI usage at 6 months	Treatment success will be defined by $\geq 50\%$ of TIF patients that has a clinically significant reduction, i.e. from "daily" PPI use to "none" or "occasional" use, at 6 months.

12. Risks

The following risks are anticipated and can result from the TIF procedure or general anesthesia:

Expected typical risks or discomfort:

- Pharyngolaryngeal pain (e.g., sore throat)
- Musculoskeletal pain (e.g., left shoulder pain)
- Temporary epigastric or abdominal pain, which can be treated with standard pain medication
- Temporary dysphagia (i.e., difficulty swallowing) due to swelling
- Nausea or vomiting

Unusual risks or discomfort:

- Oral or dental injury
- Bleeding
- Bloating sensation
- Hematoma

Rare risks:

- Esophageal perforation, laceration or tear
- Aspiration, hypoxia, achalasia

- Nerve damage
- Arrhythmia
- Pneumothorax, chest pain
- Pneumoabdomen
- Fistula
- Infection of the mediastinal space

Additional risks:

- Operation to remove a defective device or its parts
- Reoperation after a failed procedure (insufficient symptom relief)

13. Adverse Events

All adverse events will be monitored from the time of enrolling through the 6-month follow-up visit. Unanticipated adverse device effects (UADE) and SAEs will be monitored through the 12-month follow-up.

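### Section 10.2.2 tests against a fixed 24% but calls a pass non-inferior to RESPECT, and at the stated pass mark of 18/50 a two-trial comparison does not support that claim

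*Combined protocol and SAP*

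**What the plan says.** The primary hypothesis in the Synopsis, repeated in Section 5.1, is comparative: at 6 months, "the proportion of TIF patients with normalized esophageal acid exposure will be statistically non-inferior to results from the EGS RESPECT study". Section 3 says the comparison with RESPECT is made "to demonstrate equivalent (non-inferior) effectiveness". Table 5 defines primary success as a proportion of patients "with normalized acid exposure that is non-inferior to the RESPECT result as defined in 10.2.2".

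Section 10.2.2 supplies the test. It notes that "44% was observed in the EGS RESPECT study", subtracts 20 points, and sets the null hypothesis at a HEURISTIC rate of 24% or less. It then states: "The HEURISTIC normalization rate will be considered non-inferior to the 44% RESPECT rate if" that null is rejected at one-sided p < 0.05 by exact binomial calculation. With 50 evaluable patients this needs at least 18 successes (36%). The Sample Size and Power Estimation section repeats the 18/50 mark and gives power 0.90 at a true rate of 44%.

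The plan gives no numerator, denominator or interval for the 44%. The only RESPECT group size is in Table 2: 80 patients in the TIF/placebo group.

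**The concern.** A test of HEURISTIC alone against 24% controls error for one statement: the true HEURISTIC rate is above 24%. The plan's hypothesis is a different statement, that HEURISTIC is not more than 20 points worse than RESPECT. The two coincide only if RESPECT's true rate is exactly 44%. Because the 44% was observed in a finite sample, the 5% level does not carry over to the comparison with RESPECT.

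What is at stake is the conclusion at the protocol's own pass mark. A result of 18/50 would be reported as statistical non-inferiority to RESPECT. A reader would take that as a comparison with controlled error across the two trials.

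**Working it through.** **Inputs.** From Section 10.2.2 and the sample-size section: n = 50, null 24%, margin 20 points, one-sided 0.05, assumed true rate 44%, pass mark 18. From Table 2: RESPECT TIF group n = 80. Assumptions: the 44% is that group's 6-month rate, and its denominator is 80 or fewer. The count nearest to 44% of 80 is 35 (43.75%).

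**1. The plan's own figures.** P(X ≥ 18 | 50, 0.24) = 0.038 and P(X ≥ 17 | 50, 0.24) = 0.072, so 18 is the correct minimum. P(X ≥ 18 | 50, 0.44) = 0.901. Both stated figures reproduce. The exact one-sided 95% lower limit for 18/50 is 24.7%, only 0.7 points above the floor.

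**2. The difference at 18/50, with error in both trials.** The estimate is 0.3600 - 0.4375 = -0.0775.

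- Wald: SE = √(0.36×0.64/50 + 0.4375×0.5625/80) = √(0.004608 + 0.003076) = 0.0877. Lower bound = -0.0775 - 1.645×0.0877 = -0.222.
- Newcombe: the one-sided Wilson limits are 0.2582 (lower, 18/50) and 0.5293 (upper, 35/80). Lower bound = -0.0775 - √((0.3600 - 0.2582)² + (0.5293 - 0.4375)²) = -0.0775 - 0.1371 = -0.215.

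**3. The lowest passing results** (one-sided 95% lower bound, points):

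| HEURISTIC | vs 35/80, Wald | vs 35/80, Newcombe | vs 26/59, Wald | vs 26/59, Newcombe |
|---|---|---|---|---|
| 18/50 | -22.2 | -21.5 | -23.5 | -22.8 |
| 19/50 | -20.3 | -19.6 | -21.6 | -21.0 |
| 20/50 | -18.4 | -17.8 | -19.7 | -19.1 |

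With RESPECT at 44% of 80, Agresti-Caffo, Farrington-Manning and Miettinen-Nurminen bounds also fall below -20 at 18/50.

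**4. Sensitivity to the unknown denominator.** Over every count with n = 41 to 80 that rounds to 44%, the bound at 18/50 runs from -22.1 to -25.0 (Wald) and from -21.4 to -24.3 (Newcombe). At exactly 44%, 18/50 would clear -20 only if RESPECT had about 345 patients (Wald) or 168 (Newcombe). At 20/50 both methods clear the margin for all such counts with n = 55 to 80. Below 55, Wald can miss: against 22/50 the bound is -20.2.

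**5. Error rate for the claim as worded.** Suppose HEURISTIC is truly 20 points worse than RESPECT. With the floor fixed at 24%, P(X ≥ 18) is:

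| True RESPECT rate | True HEURISTIC rate | P(pass) |
|---|---|---|
| 40% | 20% | 0.6% |
| 44% | 24% | 3.8% |
| 48% | 28% | 13.6% |
| 50% | 30% | 22% |

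All four RESPECT rates lie inside the 95% Wilson interval for 44% of 80 (34% to 55%). A second view repeats both trials, sets the floor each time at the RESPECT result minus 20 points, and takes the true rates as 44% and 24%. The false-positive rate is then about 10% at RESPECT n = 80 and 11% to 13% at about 60.

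**6. How often it matters.** At a true rate of 44%, P(X = 18) = 0.060 and P(X = 18 or 19) = 0.140.

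**7. Power of the comparative claim** (true 44% in both trials, n = 50 and 80). Averaged over sampling in both trials it is 0.72 (Wald) or 0.75 (Newcombe). With RESPECT held at 35/80 it is P(X ≥ 20) = 0.76 (Wald) or P(X ≥ 19) = 0.84 (Newcombe). The stated 0.90 applies only to the test against 24%.

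**The case against.** The best defence is that nothing is hidden. Section 10.2.2 prints both hypotheses with the 24% written out, defines its use of non-inferior by that test, and Table 5 refers back to it. A fixed performance goal is a normal choice for a single-arm trial. The arithmetic is right, and Section 10.2.1 already requires 95% confidence intervals: at 18/50 the exact interval is 22.9% to 50.8%, so a borderline result would be visible. On this view the point is terminology and affects few results.

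Much of this stands. The test is legitimate and can stay. The reach is small: only 18/50 fails by every method tried. At 19/50 with 35/80 Newcombe clears and Wald does not; with 35/79 Newcombe also misses (-20.2). The recalculated-floor error rates describe a hypothetical repetition of both trials, since the plan's floor is fixed. The exact size depends on a denominator that the documents do not give.

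It does not rescue the label. The Synopsis and Section 5.1 claim statistical non-inferiority to RESPECT's results, with no qualification that RESPECT is treated as known without error. The interval required by Section 10.2.1 is for HEURISTIC alone and says nothing about RESPECT's error.

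**Conclusion.** The concern holds. The primary test is sound as a test against 24% and is mislabelled as non-inferiority to RESPECT. At 18/50 the two-trial lower bound is about 1.5 to 2 points beyond the 20-point margin with RESPECT at 35/80, and further beyond it for most smaller denominators; no count from n = 41 to 80 that rounds to 44% brings it inside. At 19/50 the conclusion depends on the interval method and the RESPECT counts. From 20/50 the two criteria agree if RESPECT had about 55 to 80 evaluable patients.

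This rests on two assumptions: that the 44% is the RESPECT TIF group's 6-month rate, and that its denominator is no larger than the 80 in Table 2. The plan should be corrected, but the issue bears only on what may be claimed from a borderline pass.

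**What to change.** Keep the exact binomial test and its 18/50 pass mark. The mark and the 0.90 power hold for 50 evaluable patients and must be recalculated if fewer are evaluable: with 48, the mark is 18/48 and power is 0.85.

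- In the Synopsis, Section 3, Section 5.1, Section 10.2.2 and Table 5, restate primary success as a 6-month normalization rate above a 24% performance goal derived from RESPECT (44% minus 20 points).
- State the RESPECT numerator and denominator behind the 44%.
- Add a supportive analysis: the HEURISTIC minus RESPECT TIF-group difference with a one-sided 95% lower bound (two-sided 90% interval), from the actual RESPECT counts, with the interval method named in advance.
- Claim non-inferiority to RESPECT only if that bound is above -20 points.
- State that neither analysis removes bias from comparing non-concurrent trials.

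The cost is wording in five places and one interval from existing counts, with no change to the sample size or the primary test. The price is a more modest headline. If the sponsor keeps the comparative claim, its power must be stated separately: at RESPECT n = 80 about 0.72 to 0.76 (Wald) or 0.75 to 0.84 (Newcombe).

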10.2.3 Safety Analysis

Treatment emergent adverse events, i.e. adverse events occurring during or after the first protocol procedure (i.e. hiatal hernia reduction), will be summarized. The proportion of patients with medically significant adverse events will be compared to the same proportions observed in the RESPECT study.

In addition, the number and proportion of subjects reporting any given adverse event, including any clinically significant hiatal hernia repair complications and new onset symptoms (dysphagia, gas bloat) should they occur, will be tabulated. Separate tables will be constructed for (a) all reported treatment emergent adverse events, (b) protocol procedures (hiatal hernia reduction, TIF) related adverse events, and (c) serious adverse events.

10.1. *Sample Size and Power Estimation*

For the primary endpoint, proportion of patients with normalized esophageal acid exposure at 6 months post TIF procedure, 44% was observed in the EGS RESPECT study. It is assumed that the true underlying rate for HEURISTIC treatment would be the same, i.e. 44%. In order to reject an inferior normalization rate of 24% at a 1-sided $p < 0.05$ level, the observed 6-month normalization rate in HEURISTIC must be 18/50 (36%) or higher. With 50 evaluable subjects, the chance (power) for successfully reaching this goal is 0.90.

11. Clinical Effectiveness Endpoints and Evaluation Criteria

11.1. *Clinical effectiveness*

Primary effectiveness endpoint and evaluation criterion

The primary efficacy endpoint is normalization in esophageal acid exposure at 6 months post TIF procedure. Normalization in esophageal acid exposure is defined as $\leq 5.3\%$ of time with $\text{pH} < 4$ in a 48-hour monitoring period.

Secondary effectiveness measures and evaluation criteria

Secondary effectiveness measures include free of “troublesome” heartburn and/or regurgitation symptoms and a clinically significant reduction in PPI use.

Per Montreal Consensus definition, troublesome symptoms are mild to severe symptoms which occur a minimum of 2 days a week.

A clinically significant PPI consumption reduction is defined as from daily use to occasional use or none at all. Daily use is defined as a double dose, or full dose or half dose taken daily for more than 80 % of the total number of days during the proceeding follow-up period.

Table 5. Study Effectiveness Endpoints and Success Criteria

Study Endpoints/Outcomes	Control	Pre-procedure Value	Post-procedure Value	Success Criteria
PRIMARY EFFECTIVENESS				
Normalized acid exposure	Self-Comparison	BRAVO Ph studies after off anti-secretory meds ≥ 7 days	BRAVO Ph studies at 6 months after off anti-secretory meds ≥ 7 days	Treatment success will be defined by a proportion of TIF patients with normalized acid exposure that is non-inferior to the RESPECT result as defined in 10.2.2.
SECONDARY EFFECTIVENESS				
GERD symptoms	Self-Comparison	Reflux Disease Questionnaire (RDQ) scores	Reflux Disease Questionnaire (RDQ) scores at and 6 months	Treatment success will be defined by a proportion of TIF patients free of troublesome symptoms at 6 months that is \geq the same proportion in RESPECT Trial (67%)
PPI usage	Self-Comparison	PPI usage (must be "daily")	PPI usage at 6 months	Treatment success will be defined by $\geq 50\%$ of TIF patients that has a clinically significant reduction, i.e. from "daily" PPI use to "none" or "occasional" use, at 6 months.

12. Risks

The following risks are anticipated and can result from the TIF procedure or general anesthesia:

Expected typical risks or discomfort:

- Pharyngolaryngeal pain (e.g., sore throat)
- Musculoskeletal pain (e.g., left shoulder pain)
- Temporary epigastric or abdominal pain, which can be treated with standard pain medication
- Temporary dysphagia (i.e., difficulty swallowing) due to swelling
- Nausea or vomiting

Unusual risks or discomfort:

- Oral or dental injury
- Bleeding
- Bloating sensation
- Hematoma

Rare risks:

- Esophageal perforation, laceration or tear
- Aspiration, hypoxia, achalasia

- Nerve damage
- Arrhythmia
- Pneumothorax, chest pain
- Pneumoabdomen
- Fistula
- Infection of the mediastinal space

Additional risks:

- Operation to remove a defective device or its parts
- Reoperation after a failed procedure (insufficient symptom relief)

13. Adverse Events

All adverse events will be monitored from the time of enrolling through the 6-month follow-up visit. Unanticipated adverse device effects (UADE) and SAEs will be monitored through the 12-month follow-up.

An AE is defined as any undesirable clinical occurrence in a patient whether or not it is considered to be device related. In addition, the definition of AE applies to any event with an onset post study treatment or to any underlying diseases, present at baseline, that exacerbate in severity post study treatment. Therefore, an underlying disease that was present at the time of enrollment is not reported as an AE, but any increase in the severity of the underlying disease is to be reported as an AE. This definition includes events occurring during the follow-up period.

All AEs must be recorded in the electronic database. A description of the event, including the start date, resolution date, action taken, and the outcome should be provided, along with the Investigator's assessment of the relationship between the AE and the study treatment.

A serious adverse event (SAE) is defined as an event which leads to:

- Death due to any cause
- Life-threatening condition
- Results in persistent or significant disability/incapacity
- Requires in-patient hospitalization or prolonged hospitalization
- Necessitates an intervention to prevent a permanent impairment of a body function or permanent damage to a body structure
- Results in congenital abnormality

